#### Stat-3 RNA levels and phosphorylation status in NK cells and tumor tissue before and after metformin, pembrolizumab and combination treatment.

Metformin has previously been postulated to inhibit tumor development by reducing insulin/IGF-1 signaling, in turn preventing the release of pro-inflammatory cytokines through NF- $\kappa$ B and enhancing the anti-cancer immune response mediated by NK cells and cytolytic T-

cells. In addition, STAT3 which can be inhibited by metformin as mentioned above, is important for NK cytolytic functions. Our work has shown that metformin does indeed reduce STAT-3 expression and phosphorylation in a HNC cell line (SCC-47). In Fig. 3, we show that metformin reduces pS6 which is downstream from mTOR and known to be decreased by metformin but that metformin also results in pSTAT3 decrease. Our hypothesis is that metformin reduces Stat-3 expression in patient tumor cells as well as immune cells. It is unclear if pembrolizumab will result in any additive effect. Therefore, tissue will be examined for Stat-3 expression in both immune cell populations and tumor cells.

### NKG2D soluble ligands before and after metformin, pembrolizumab and combination in the plasma.

NKG2D, an important activating receptor on NK cells, can be inhibited by NKG2D soluble ligands. In addition, HNSCC patients with high levels of such a ligand, sMICA, carry a poor prognosis. NK cells express both inhibitory (killer cell Ig-like receptors or KIRs and CD94-NKG2A) and activation receptors (e.g., NKG2D). Inhibitory receptors bind MHC-1 which is often lost on cancer cells rendering cancer cells more susceptible to NK dependent killing. Cytokines (interleukin-2 and -15) can lower the threshold of NK activation and may be activated by singular receptors (NKG2D) in order to trigger effector functions. Understanding the interplay between activation and inhibition of NK cells is critical and may give the ability to exploit NK cells to better harness the benefits of immunotherapy. Here we hypothesize that patients able to express higher levels of NKG2D will also have lower levels of sMICA in the peripheral blood.

## **PATIENT SELECTION**

### **4.1 Eligibility Criteria**

1. Patients must have histologically or cytologically confirmed recurrent or metastatic non-cutaneous HNSCC for which there are no surgical or radiation curative options.
2. Patients may have received up to 3 prior lines of therapy for metastatic or recurrent disease.
3. Age  $\geq 18$  years.
4. ECOG performance status  $\leq 2$  (Karnofsky  $\geq 60\%$ , see Appendix A).
5. Patients must have adequate organ and marrow function as defined below:
 

– leukocytes	$\geq 3,000/\text{mcL}$
– absolute neutrophil count	$\geq 1,000/\text{mcL}$
– platelets	$\geq 75,000/\text{mcL}$
– total bilirubin	$\leq$ institutional 1.5x upper limit of normal (ULN)

- AST(SGOT)/ALT(SGPT)  $\leq 3 \times$  institutional ULN
  - creatinine  $\leq 1.5 \times$  institutional ULN
  - OR
  - glomerular filtration rate (GFR)  $\geq 50$  mL/min/1.73 m^2 (see Appendix B).
6. Human immunodeficiency virus (HIV)-infected patients on effective anti-retroviral therapy with undetectable viral load within 6 months are eligible for this trial.
  7. For patients with evidence of chronic hepatitis B virus (HBV) infection, the HBV viral load must be undetectable on suppressive therapy, if indicated.
  8. Patients with a history of hepatitis C virus (HCV) infection must have been treated and cured. For patients with HCV infection who are currently on treatment, they are eligible if they have an undetectable HCV viral load.
  9. Patients with treated brain metastases are eligible if follow-up brain imaging after central nervous system (CNS)-directed therapy shows no evidence of progression for at least 4 weeks.
  10. Patients with new or progressive brain metastases (active brain metastases) are eligible if the treating physician determines that immediate CNS specific treatment is not required and is unlikely to be required during the first cycle of therapy.
  11. Patients with a prior or concurrent malignancy whose natural history or treatment does not have the potential to interfere with the safety or efficacy assessment of the investigational regimen are eligible for this trial.
  12. Patients with known history or current symptoms of cardiac disease, or history of treatment with cardiotoxic agents, should have a clinical risk assessment of cardiac function using the New York Heart Association Functional Classification. To be eligible for this trial, patients should be class 2B or better.
  13. Female subjects of childbearing potential should have a negative urine or serum pregnancy within 72 hours prior to receiving the first dose of study medication. If the urine test is positive or cannot be confirmed as negative, a serum pregnancy test will be required.
  14. Female subjects of childbearing potential should be willing to use 2 methods of birth control or be surgically sterile, or abstain from heterosexual activity for the course of the study through 4 months after the last dose of study medication. Subjects of childbearing potential are those who have not been surgically sterilized, or have not been free from menses for > 1 year.
  15. Male subjects should agree to use an adequate method of contraception starting with the first dose of study therapy through 4 months after the last dose of study therapy.

16. Must have adequate archival baseline tissue available (see tissue requirements) or new biopsy must be performed (section 6.2).

17. Ability to understand and the willingness to sign a written informed consent document.

## 4.2 Exclusion Criteria

1. Patients with nasopharyngeal HNSCC will be excluded.
2. Patients who have had chemotherapy or radiotherapy within 2 weeks prior to entering the study. Palliative radiotherapy is allowable and does not require washout. Palliative radiotherapy on study is allowed as long as it is not to target lesions.
3. Patients who have not recovered from adverse events due to prior anti-cancer therapy (i.e., have residual toxicities > Grade 1) with the exception of alopecia. Grade 2 neurotoxicity is allowable as long as clinically stable.
4. Patients who are receiving any other investigational agents.
5. Patients who have previously received PD-1 or PD-L1 inhibitors for metastatic/recurrent disease. Treatment in the curative setting is allowable.
6. Patients currently receiving metformin or who have received metformin in the last 6 months.
7. History of allergic reactions attributed to compounds of similar chemical or biologic composition to pembrolizumab or metformin.
8. Patients may not receive any medication or substance that is known to be strongly associated with lactic acidosis (ex. NRTIs, see Appendix C) within 14 days of initiating metformin ER treatment.
9. Patients with uncontrolled intercurrent illness that in the opinion of the investigator will prohibit compliance with the study.
10. Patients with psychiatric illness/social situations that would limit compliance with study requirements in the opinion of the investigator.
11. Requirement of any use of steroids greater than the equivalent of 10mg prednisone daily is not allowed.
12. Patients with history of autoimmune diseases currently requiring systemic immunosuppressive treatment in addition to, or instead of, steroids are excluded.
13. Pregnant women are excluded from this study because there is an unknown but potential

risk for adverse events in nursing infants secondary to treatment of the mother with pembrolizumab. Breastfeeding should be discontinued if the mother is treated with pembrolizumab.

14. Patients that are unable to swallow pills will be excluded as metformin ER cannot be crushed. PEG tube is allowable as long as patients are able to swallow pills.
15. Patients cannot receive live vaccines within 30 days prior to the first dose of trial treatment. Examples of live vaccines include, but are not limited to, the following: measles, mumps, rubella, varicella/zoster, yellow fever, rabies, BCG, and typhoid vaccine.

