### 3.2.2 Metformin

Activation of the PI3K, Akt and the mammalian target of rapamycin complex 1 (mTORC1) signaling pathway was identified as being a prevalent molecular signature in many HNSCCs, resulting in potential strategies to target this pathway. In fact, activating mutations of the mTOR pathway are now recognized as drivers of some HNSCCs. However, targeting the mTOR pathway with rapamycin analogues, such as everolimus, results in undesirable side effects including mucositis, thrombocytopenia, and increased infection risk making combinatorial treatment with

systemic agents such as chemotherapy and radiation difficult. Interestingly, metformin has been shown to inhibit the mTOR pathway. Metformin is a biguanide and an oral antihyperglycemic agent, which is currently FDA approved for the treatment of type II diabetes. Specifically, metformin inhibits mTORC1 activity, through activation of the AMPK pathway resulting in decreased proliferation, metabolic synthesis and metastases in breast and colon cancer. Additionally, metformin inhibits HNSCC cell growth *in vitro* and prevents development and progression of oral cavity tumors in a HNSCC mouse tumor model supporting a role for metformin as a cancer preventative. The latter study demonstrated that metformin may also inhibit mTORC1 activity independent of AMPK activation. In line with these animal studies, retrospective population case-control cohort studies have demonstrated a decreased HNSCC risk in diabetic patients treated with metformin. In addition, metformin use resulted in a better overall survival in diabetic patients diagnosed with laryngeal squamous cell carcinoma. The potential impact of metformin use in non-diabetic HNSCC patients is unknown.

Metformin is widely used in many diabetic patients and overall well tolerated. Unlike other antihyperglycemic agents such as the sulfonylureas, metformin does not usually cause hypoglycemia. Adverse effects are relatively minimal with diarrhea being the most common cause of discontinuation. However, lactic acidosis, although rare (estimated incidence of 4.3 cases per 100,000 person-years in metformin users), is a serious adverse event resulting in up to 50% mortality when it occurs. Lactic acidosis has been associated with high plasma concentrations of metformin (>10mg/ml) which can occur in the presence of renal dysfunction. Therefore, careful

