monitoring of renal function of patients on metformin is imperative to reduce the incidence of this rare side effect. However, a recent retrospective study from the United Kingdom, demonstrated that there was no increase in lactic acidosis in patients taking metformin even in patients with severe kidney dysfunction (eGFR <30ml/hr). The latter study did not measure serum metformin levels. In our phase I study using escalating doses of metformin in combination with cisplatin and radiation in locally advanced HNSCC, no incidence of increased lactic acid was seen and peak plasma concentrations of metformin at highest dose of 3000mg daily was 2585 +/- 1007 ng/ml. However, it should be noted that Metformin was held for Cr >1.5 in the latter study. No incidence of hypoglycemia was observed. Survival outcomes in this small phase I study were impressive with 90% 2 year overall survival. Importantly, many patients discontinued Metformin due to nausea and/or diarrhea most often at the highest dose of 3000mg daily but also at doses of 2550mg daily. Peak concentrations of patients from cohort one (2000mg daily) was 2045 +/- 1022 ng/ml with interpatient variability. However, given the range of peak concentrations between the three cohorts and the increase in toxicity of higher cohorts, in this current study, we have chosen to use the 2000mg daily dose. Metformin ER which is an extended release form of metformin will be used on this study as it has been shown to cause less side effects and will allow for better treatment compliance. Therefore, the standard dose will be 2000mg daily of metformin ER.

[figure not shown]

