#### 7.4.1 Metformin

##### *Treatment:*

Patients will receive metformin ER starting on day -14 for arm 1 and Day -7 for arm 2. The starting dose will be 1000mg PO daily to be administered with evening meal. The tablet should be swallowed whole, and patients will be instructed not to crush, cut or chew medication. On day -7 (or Day 1 for arm 2), patients will increase to 2000mg daily. Metformin will be continued daily with pembrolizumab.

Metformin should continue throughout treatment and even through pembrolizumab delays unless patient is experiencing adverse effects attributed to metformin. Metformin should be taken with food at approximately the same time daily. Patients will be instructed to check their blood sugar if they have any symptoms of hypoglycemia including but not limited to chills/shakiness, cold feeling, lightheadedness, dizziness, etc. Patients will be given a diary to record each dose. They should also be warned that the shell of the ER tablet may be visible in stool and not to be alarmed.

NOTE: Temporarily discontinue metformin in patients undergoing radiologic studies in which intravascular iodinated contrast media are utilized. It is generally recommended that metformin be temporarily discontinued prior to or at the time of intravascular administration of iodinated contrast media (potential for acute alteration in renal function). Continue to withhold metformin for 48 hours after the radiologic study.

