## 7.8 General Concomitant Medication and Supportive Care Guidelines

Metformin and pembrolizumab are not affected by p450 enzymes and therefore p450 inhibitors are allowed.

Concomitant use of furosemide results in increased levels of metformin and therefore should be avoided if possible but is allowable if needed for diuresis with close monitoring.

Cationic drugs (e.g., amiloride, digoxin, morphine, procainamide, quinidine, quinine, ranitidine, triamterene, trimethoprim, or vancomycin) that are eliminated by renal tubular secretion

theoretically have the potential for interaction with metformin by competing for common renal tubular transport systems. Therefore, these medications are to be avoided if possible while patient is on study but are allowable if felt to be necessary by patient's physician. However, it must be documented that patient was on these medications.

Nifedipine results in enhanced absorption of metformin. It must be documented if a patient is on nifedipine during the study but is allowable.

Subjects are prohibited from receiving the following therapies during the Screening and Treatment Phase of this trial:

- Biological therapy
- Immunotherapy not specified in this protocol
- Chemotherapy
- Investigational agents other than pembrolizumab or metformin
- Live vaccines within 30 days prior to the first dose of trial treatment and while participating in the trial. Examples of live vaccines include, but are not limited to, the following: measles, mumps, rubella, varicella/zoster, yellow fever, rabies, BCG, and typhoid vaccine.
- Systemic glucocorticoids should be avoided if possible. Steroids are allowed as short bursts of 5-7 days if required for clinical indication (i.e. COPD) or to modulate symptoms from an adverse event of suspected immunologic etiology. The chronic use of physiologic doses of corticosteroids may be approved after consultation with the Sponsor Investigator.

Subjects, who, in the assessment by the investigator, require the use of any of the aforementioned treatments for clinical management other than specified as allowed, should be removed from the trial. Subjects may receive other medications that the investigator deems to be medically necessary.

There are no prohibited therapies during the Post-Treatment Follow-up Phase.

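### The bar on lactic-acidosis drugs (exclusion item 8, Appendix C) ends within about two weeks of starting metformin, and section 7.8 is silent on them: a minor gap that a few sentences would close

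*Combined protocol and SAP*

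**What the plan says.** Section 4.2, item 8, excludes use of drugs strongly linked to "lactic acidosis (ex. NRTIs, see Appendix C) within 14 days of initiating metformin ER treatment". Appendix C lists 13 antiviral products or combinations and contains no rule of its own.

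On dosing, section 7.4.1 states: "Patients will receive metformin ER starting on day -14 for arm 1 and Day -7 for arm 2". It adds: "Metformin will be continued daily with pembrolizumab". Under section 7.9, treatment runs until progression or another stopping criterion.

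Section 7.8 covers medication during treatment. It deals with p450 inhibitors, furosemide, cationic drugs and nifedipine, and then lists prohibited therapies. Appendix C, NRTIs and lactic acidosis do not appear. Two of its general sentences matter here. Patients who "require the use of any of the aforementioned treatments for clinical management other than specified as allowed, should be removed from the trial". For everything else: "Subjects may receive other medications that the investigator deems to be medically necessary".

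On the hazard, section 3.2.2 describes lactic acidosis as, "although rare (estimated incidence of 4.3 cases per 100,000 person-years in metformin users), is a serious adverse event resulting in up to 50% mortality". Of the sponsor's phase I study it reports that "no incidence of increased lactic acid was seen". Section 8.1 requires permanent discontinuation of metformin once lactic acidosis has occurred.

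**The concern.** The hazard behind item 8 is taking a listed drug together with metformin, and that hazard lasts as long as metformin does. The rule, however, is tied to the start of metformin. After its short window, an investigator who consults the protocol about a new antiviral finds only the medical-necessity clause of 7.8.

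The rest of 7.8 suggests an oversight. The live-vaccine exclusion is carried over as a continuing bar: "Live vaccines within 30 days prior to the first dose of trial treatment and while participating in the trial". Cationic drugs, whose interaction the protocol calls theoretical, get an on-study instruction to avoid them if possible and to document their use. The Appendix C drugs, which the protocol treats as a stronger hazard, get none.

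What is at stake is the safety of an occasional patient. No estimate or test in the statistical plan depends on it.

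**Working it through.** The plan gives no figure to reproduce beyond the 14-day window. The check compares that window with metformin exposure and then sizes the risk.

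**1. Where the bar ends.** Item 8 does not say whether its 14 days lie before the start of metformin, after it, or both.
- Before only (a wash-out): the bar ends at the first metformin dose.
- Both sides: the bar covers metformin days 1 to 14, or 1 to 15 on an inclusive count. With no Day 0, metformin day 15 is Day 1 in Arm 1 (start Day -14) and Day 8 in Arm 2 (start Day -7).

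Under 7.4.1 the 2000 mg dose begins on metformin day 8 in both arms. Even the wider reading therefore covers only about one week at full dose.

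**2. Metformin days outside the bar.** Treatment duration is not fixed, so I assume 12 to 52 weeks (84 to 364 days) from Day 1.
- Arm 1: 14 + 84 = 98 days, up to 14 + 364 = 378 days.
- Arm 2: 7 + 84 = 91 days, up to 7 + 364 = 371 days.
- Two-sided reading: from 91 − 15 = 76 to 378 − 14 = 364 days have no bar.
- Wash-out reading: all 91 to 378 days have no bar.

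These are calendar days without a written rule. They are not days of co-exposure and do not measure risk.

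**3. Last scheduled lactate.** The Study Calendar schedules lactate at screening, Cycle 1 Day 1 and Cycle 2 Day 1. Cycle 2 Day 1 is Day 22, which is metformin day 14 + 22 = 36 in Arm 1 and 7 + 22 = 29 in Arm 2.

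**4. Background risk.** Expected cases = patients × years on metformin × 4.3/100,000 (rate from 3.2.2).
- Shortest: 25 × 91/365.25 = 6.23 person-years, giving 0.00027 cases.
- Longest: 25 × 378/365.25 = 25.87 person-years, giving 0.0011 cases. At up to 50% mortality, that is at most about 0.0006 deaths.

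This is the rate in metformin users generally.

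**5. Risk with a listed drug.** The documents give no multiplier. I assume that 1 to 2 patients start a listed drug for one year and that it raises the rate 1- to 100-fold.
- Low: 1 × 0.000043 = 0.00004 cases.
- High: 2 × 0.0043 = 0.0086 cases.

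Even the high end is below 0.01.

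**6. Who is exposed.** Item 8 already stops a patient who is taking a listed drug at entry. What remains is a new start during treatment, for example a patient with chronic hepatitis B whose suppressive therapy becomes indicated after entry (section 4.1, item 7). Because item 7 requires an undetectable viral load at entry, this group is small. The documents do not state its size.

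**The case against.** The strongest reply is that this matters very little. The expected number of cases is tiny, and the upper figure needs a 100-fold multiplier that no document supplies. Item 8 and Appendix C already tell investigators which drugs are a worry with metformin. Leaving a rare new start to clinical judgement also fits 7.8, which allows furosemide and cationic drugs when needed. All of this stands as to size.

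There are also safeguards:
- Sections 7.4 and 9 refer sites to the metformin package insert and require that a current version be available. Its content on these drugs cannot be checked from the documents.
- Concomitant medication is recorded (7.2), and unscheduled tests are allowed (section 7).
- Metformin is halved or held by eGFR (8.1), and bicarbonate and creatinine are part of the chemistry taken each cycle.
- The DSMB reviews safety (14.3.1).

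These narrow the gap, but no rule in the protocol itself tells an investigator not to combine a listed drug with metformin.

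A reader might infer more than the text supports, in three ways:
- *That 7.8 expressly permits these drugs.* It does not. It is silent, and only the general medical-necessity clause applies.
- *That HIV patients on anti-retroviral therapy (4.1, item 6) are the exposed group.* Their position turns on the conflict between inclusion items 6 and 7 and exclusion item 8, which concerns who may enter. Settling it would not by itself say what may be started later.
- *That the long uncovered period means substantial risk.* Step 2 counts days without a rule, and only a patient who starts a listed drug in that time is exposed.

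**Conclusion.** The gap is real and minor. On either reading of item 8, the only rule applying Appendix C has ended by about metformin day 15 or 16. Nothing in 7.8 replaces it while metformin continues. Few if any of the 25 patients would be affected, the absolute risk is very low, and the primary analysis is untouched. The case for acting is that the outcome is grave when it occurs, the sponsor already thought the risk worth an exclusion, and the correction costs almost nothing.

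This rests on assumptions that the documents do not settle: 12 to 52 weeks of treatment, at most 1 to 2 new starts, a 1- to 100-fold effect of a listed drug, and no relevant rule on the schema page, which I could not see. Within those ranges the rating does not change.

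**What to change.** - In 7.8, state that Appendix C drugs are not to be taken with metformin from 14 days before the first metformin dose through the last, in both arms. Word item 8 to match, which also settles the direction of its window.
- State that if a listed drug becomes necessary, metformin is stopped, while pembrolizumab and follow-up may continue. Make this an express exception to the 7.8 removal sentence. Otherwise, adding the drugs to the prohibited list would take the patient off the trial.
- State that evaluability is unchanged under 13.1.1: toxicity from the first dose, and response on the existing terms.
- Make the edit together with the resolution of inclusion items 6 and 7 against exclusion item 8, so that any antiviral allowed at entry is also allowed in 7.8.

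The cost is a few sentences, with no new visit or test. Section 7.3.5 already provides for consultation on metformin interruptions longer than 4 weeks. The downside is that an occasional patient has less combination exposure, and a later response on pembrolizumab alone would still count toward the response rate. That already happens when metformin is stopped for toxicity under 8.1, since 13.1.1 does not require metformin to continue, so no new bias is added. Any such patient should be reported.
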